## **1. BACKGROUND**

According to the World Health Organization, 50 million people worldwide have dementia with an annual incidence of 10 million new cases every year. Individuals diagnosed with mild cognitive impairment (MCI), specifically those with primary amnestic/memory loss (aMCI), are one of the highest risk groups for conversion to dementia, with approximately 34% developing dementia within one year. Prevention strategies for cognitive decline are critical during this risk period. The lack of medical treatments able to stop or slow down the development of dementia has shifted the research field focus towards the urgent need to develop preventative, non-pharmacological approaches and psychosocial therapies for people at-risk for the disease.

Both cognitive remediation and exercise training strategies have been developed for interventions in MCI patients and show small but not yet definitive improvements on cognition. A large body of evidence suggests that regular physical exercise can improve cognition, specifically enhancing memory, attention, and executive functions in older adults and is associated with a 35–38% reduction in the risk of cognitive decline and dementia. However, a recent meta-analysis of exercise interventions in older adults concluded there is not yet enough evidence to support the definitive benefits of exercise alone on cognition. Cognitive remediation interventions that target restoration of cognitive functioning through compensatory cognitive skills training in MCI patients show a clear advantage over the more generalized computer-based drill and practice neurocognitive training programs. In contrast, studies that implement both targeted neurocognitive and exercise training interventions

(rather than each alone) are showing greater promise on improving cognitive function in older adults as well as having real-world functioning benefits in MCI and dementia. Study PI ([name]) and Co-I ([name]) recently published the first study that attempted to leverage the synergistic benefits of simultaneously performing compensatory memory skills training during aerobic exercise (stationary aerobic cycling; SIM training) in older adults with subjective memory impairments. In our clinic-based, pilot RCT we validated the feasibility of the SIM training in older adults and found that it was more impactful on improving memory, attention and reasoning skills than in a group that performed the training separately.

Unfortunately, older adults experience extensive barriers to engaging in the aforementioned preventative practices due to mobility constraints, lack of access, and low motivation to engage in activities that are not tailored to their needs. Delivering low-cost, effective, prevention-focused interventions to cognitively impaired older adults could reduce these barriers by increasing ability, motivation, and adherence. Prior technology-enabled interventions to increase physical activity levels have included providing older adults with fitness trackers. One study conducted in older adults found that the provision of a Fitbit monitor alone to objectively track one's own activity leads to increased physical activity levels beyond those of whom are concurrently receiving coaching prompts (via text message). Consistent feedback through notifications, as well as integration with social support and competition through “leaderboards” and “rewards,” encourage participants to exercise, which led to overall increases in physical activity.. Together, studies on this technology suggest that goal setting is effective for increasing physical activity. A comprehensive review of activity trackers used in research studies “that having a fitness tracker could actually be an intervention in and of itself” and concluded that the use of fitness trackers, show a great deal of promise for measuring and encouraging physical activity. Therefore, for this pilot RCT, we will provide our “control” arm with continuous activity monitoring and provide instructions and training on device and feature usage. We anticipate an increase in their physical activity levels even without the rigorous schedule and program that our “mSIM” group is receiving. We are primarily trying to compare our intervention with “standard of care,” which normally includes clinicians advising MCI patients to increase their physical activity habits.

Animal studies provide important mechanistic insights into the benefits of exercise in improving cognition. Specifically, aerobic exercise increases the density of blood capillaries (angiogenesis) and birth of new neurons (neurogenesis). Skilled-based exercises increase neuronal sprouting and synaptogenesis, important for re-establishing brain circuits impaired in disease states and required for normal cognition. However, no study has been conducted in aMCI patients that explores the effects of memory skills training during aerobic exercise on cognition and functioning.

The underpinnings of exercise and cognitive training-induced memory improvements may lie in neurochemicals such as brain-derived neurotrophic factor (BDNF) and norepinephrine (NE). BDNF is the most widely distributed neurotrophin in the brain, with the highest density found in the hippocampus. BDNF can modulate neurogenesis, neuronal plasticity, and survival. Furthermore, increased central BDNF expression has been causally linked to the learning and memory enhancement that is seen in both cognitive training and

physical exercise interventions with animals. BDNF decreases with aging and increases with physical activity and associated memory improvements in older adults and those with MCI. NE is released by the locus coeruleus (LC) during physical activity and may be facilitating these effects also. The LC is the main source of NE during physical activity. This activates the reticular system, thus increasing arousal levels, aiding to vigilance and attention during cognitive training. LC neuronal loss is prominent in AD neuropathology and contributes to cognitive impairments. Reduced concentrations of NE are believed to occur early in the course of the illness as seen in MCI patients. Activation of the NE system during exercise may facilitate the long-term impact of memory training .

Electroencephalography (EEG) is a non-invasive method of measuring the electrical activity of the brain. Quantitative EEG (QEEG) is a method for recording and analyzing EEG data efficiently in a clinical setting. The brain has many brain rhythms, each associated with different mental states. As more populations of neurons act in greater synchrony, the amplitudes of these rhythms increase. The Alpha rhythm is 8-12 Hz and was originally identified as a resting state/idling brain rhythm. More advanced models show that Alpha is important for the inhibitory tone of the brain. Higher alpha power means more brain systems are being inhibited, whereas a low Alpha power means the brain is experiencing less inhibition, allowing for the engagement of more active states. Alpha plays a critical role in the timing of neurological and cognitive processes including working memory, attention, and anticipation. These and more decline with age and neuropathology. Peak Alpha frequency slows with age and is correlated with cognitive decline. In older adults with poorer cognition, there is a greater degree of slowing in the Alpha band.

GABA is the neurotransmitter in the brain primarily responsible for inhibition. Animal studies show potential mechanisms by which exercise may improve cognition by restoring inhibitory tone. Mice that carry the APOE4 gene are, like humans, at risk for Alzheimer's. These mice have hyperexcitable brains when compared with normal mice. They experience dysregulated and increased brain activity because they do not respond to their native GABAergic networks as well as normal mice. Another study, this time in aged rats, demonstrated that an aerobic fitness intervention was able to reduce the age-related hyperactivity in the rat brain and worked through improving the GABAergic system^38. Increases in peak Alpha frequency may be a result of the mSIM intervention in humans and these findings could be mediated by the normalization of GABA-related signaling post intervention.

## **2. OBJECTIVES OF THE STUDY**

One major study objective is to develop and conduct beta testing of a web-based application that will deliver a mobile-based simultaneous exercise and memory skills training program (mSIM) for aMCI patients. A second major objective of the study is to evaluate the efficacy of mSIM on memory performance and everyday functioning using two study arms: Group 1 or the activity monitoring control group (CON) and Group 2 or the activity monitoring plus

immediate treatment with the mSIM intervention group (mSIM). The CON will serve as the control group and be recommended to wear a Fitbit to track their physical activity habits, which has been shown to be an effective intervention to increase physical activity levels, throughout the duration of the intervention. They will also report one week's physical activity via phone calls with research staff at baseline, mid-intervention, and post-trial. Study objectives include measuring treatment related changes in quality of life and cognitive and functional abilities.

A third major objective of this study is to test mSIM treatment response on concentration levels of peripheral biomarkers [BDNF and NE] and neural markers (eg. peak alpha frequency) measured with QEEG. Study objectives include testing the relationship between increased peak alpha frequency, concentrations in BDNF and NE, and improvements in memory.

An exploratory objective of this study is to test treatment response to the mSIM intervention using magnetic resonance imaging (MRI). We will analyze functional resting state fMRI, structural MRI, arterial spin labelling (ASL) and diffusion tensor imaging (DTI) data for this study. We hypothesize that patients in the mSIM intervention, compared to the controls, will have increased default mode network (DMN) connectivity, increased frontal and temporal volumes, and increased temporal perfusion. We will seek to examine exploratory measures on structural connectivity using DTI. It is believed that the white matter deficits precede grey matter neuronal loss in preclinical AD since neuronal degradation begins in neuronal periphery, which consists of axons and dendrites. A meta-analysis of 41 DTI studies in MCI and AD revealed almost all white matter tracts are implicated in the disease state. Limbic fibers, which have direct connections to the medial temporal lobe, had reduced integrity. Additionally, the cingulum bundle, mainly within the medial temporal lobe, the splenium of the corpus callosum, and the fornix were all reduced and were correlated with severity of reduced cognition as implicated on the MMSE and memory tests. The left cingulum bundle (within the hippocampus) showed decreased FA and increased MD, which were specifically associated with worse symptoms and ADAS-cog scores. Interventional exercise research in older adults has revealed that short-term exercise interventions have a positive benefit on white matter integrity in the corpus callosum. Therefore, we hypothesize that the mSIM intervention will increase white matter integrity especially in the cingulum bundle, corpus callosum, and the fornix.

### **3. STUDY DESIGN**

#### **Overview**

Participants with primarily amnestic MCI (aMCI) will be enrolled in the trial. MCI will be defined according to either the Peterson or Jak/Bondi criteria neuropsychological approach in which tests are organized by cognitive domain and criteria are set for defining impairment within any particular domain. Assessments of memory confirming diagnosis will

have occurred within 6 months prior to consent or will be conducted at screening to confirm eligibility.

### **Subject Identification and Recruitment**

Study subjects will be recruited using a variety of techniques to identify participants that meet inclusion and exclusion criteria and who are able to participate in the trial. Recruitment techniques will include (1) identification of patients from a high-volume memory clinic (PBHC), (2) advertisement to participants in the Los Angeles area, and (3) establishment of a website landing page that permits interested individuals to contact the trial coordinator. A total of up to 30 aMCI participants (50-80 years old) will be enrolled in this prospective randomized study (15 for each arm). Because there are several inclusionary/exclusionary criteria that must be assessed after obtaining informed consent, up to 60 participants may consent to participate in this study.

### **Procedures for Obtaining Informed Consent**

All subjects will receive and sign the Experimental Research Subject's Bill of Rights prior to signing the informed consent form (ICF). Subjects will also complete an authorization of use and disclosure of protected health information (PHI), and a second authorization of medical record release for the subject's treating physician, prior to enrolling in the study. A copy of all signed ICFs will be given to the subject, and the investigator will retain the originals.

### **Screening and Enrollment**

Subjects interested in participating in the study will be screened based on the inclusion and exclusion criteria listed below.

#### Inclusion Criteria

- Subjects must be age 50 to 80 at time of informed consent.
- Subjects must confirm an aMCI diagnosis either by providing records from a clinical assessment within 6 months of enrollment in this study or through a brief memory assessment by study staff at screening.
- Subjects must be proficient in spoken and written English for consenting as well as for study participation since the intervention in this study is currently only available in English.
- Subjects with medical conditions must be stable for these conditions. Stable control on medication is acceptable.
- Subjects, with or without assistance, must be able to use a computer and web interface. If assistance is needed, it must be readily available to them.
- Subjects are required to have internet with Wi-Fi at the location of their mSIM training.
- Subject must have normal visual acuity (or corrected to normal) and normal color vision as indicated by self-report.
- Subject must have adequate hearing acuity as indicated by self-report.
- Subject must have adequate motor capacity to use a mobile phone/iPad/computer as indicated by self-report.

- Subjects must be able to provide medical clearance to participate in an unsupervised, moderate intensity exercise program from a physician.

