- Group 2 (mSIM): Participant may be required to see a cardiologist for medical management as part of their standard of care if additional ischemic or hypertensive risk factors are uncovered during the physical status assessment. If participant's blood pressure continues to be above ACSM guidelines and the participant cardiologist will not clear them to participate in a moderately intense, unsupervised exercise program, the participant will be withdrawn from the study 

**Study equipment set-up**, the following will occur:

- On-going collection of lifestyle data from FitBit device
- Group 2 (mSIM): Delivery company will set up study equipment at participant's home
- Group 2 (mSIM): 2 (but up to 6\*) weeks aerobic exercise ramp-up using the exercise equipment provided

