### Mobile-Based Simultaneous Exercise and Memory Skills Training Program (mSIM):

**Figure 1.** Home set-up of the mobile technology-based simultaneous exercise and memory skills training (mSIM) program.

The mSIM intervention will be carried out in participants assigned to Group 2 (mSIM). Before the in-home training intervention can begin, a research staff member will set-up the participant's equipment while they are on site at PBHC, troubleshoot, plan exercise training days and times, and inform them of the exercise ramp-up procedures. The equipment required for the mSIM home training sessions is compact and low-cost and will include: a folding, stationary exercise bike, Fitbit heart rate and activity monitor synced to the participant's study account, and a tablet to access our mSIM web-based application (see **Figure 1**).

The mSIM participants (Group 2 (mSIM)) will begin by undergoing a minimum of 2 weeks, but up to 6 weeks if necessary, of aerobic exercise ramp-up. Participants will

wear heart rate monitors (FitBit) to self-monitor and ensure that the exercise was completed within their prescribed aerobic target heart rate zone, which is 40-60% heart rate reserve (HRR). The target heart rate zone will be determined by the Karvonen formula, which determines the individual participant's HRR and training zone. The Karvonen Formula is:

$$\begin{aligned} 220 - \text{age} &= \text{maximum heart rate} \\ \text{Maximum heart rate} - \text{resting heart rate} &= \text{heart rate reserve} \\ (\text{Heart rate reserve} \times \text{training\%}) + \text{resting heart rate} \end{aligned}$$

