The ramp-up for mSIM participants will start with 2 days per week for 2-6 weeks, where they will be asked to maintain an aerobic intensity of up to 40-60% HRR for 10-40 minutes, depending on their baseline physical activity level. After the ramp-up phase the mSIM (Group 2) participants will begin the 12-week intervention, comprised of 2 times/week, 65-minute sessions. Each mSIM session will include up to 15 minutes of sedentary new memory skills introduction learning or review. They will then have a 5-minute warm-up on the bike (30% HRR), followed by 35 minutes of memory skills training and practice while aerobic cycling in their estimated 40-60% aerobic training zone. They will then have 5 min of interval training which is continuously monitored on the FitBit wrist-worn watch. The resistance level will be pre-set on their bike to meet their aerobic training zone. They will then finish with a 5-minute cool-down that may include a 5-minute summary of skills learned in the session. Participants will be instructed in the importance of staying within their target heart rate zone and not exceeding their heart rate zone. A research staff member will be available during the first 2 weeks of mSIM training sessions via phone to help with any technical issues the participant has during the training session. Participants will be asked to open the FitBit App during their training session to sync their FitBit and indicate the start and stop time of their training session on a session log, so data can be monitored in real-time with the Fitbit data aggregator by research staff and to aggregate study compliance data. All FitBit data will use a de-identified study email address so that no personal identifying data will be linked with either FitBit or the FitBit data aggregator. Participant will be trained on how to ensure they are within their individualized 40-60% HRR and of the safety reasons for not going above 60%HRR.

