### **Medical Record Collection**

A participant's medical record will be collected from their treating physician's office at screening/baseline for medication types, dosage, and frequencies as well as other existing medical conditions and their treatment. The data will be entered into an electronic data capture system by research staff at PBHC. In the event that a particular participant's data has extreme or outlier characteristics, their medical record will be reviewed to identify explanatory factors.

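### The mSIM training zone comes from 220 minus age for everyone; for a participant whose medicine lowers maximum heart rate below that, its upper part may exceed the protocol's own 60% limit

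*Combined protocol and SAP*

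**What the plan says.** Section 3, Inclusion Criteria, on drug treatment: "Subjects with medical conditions must be stable for these conditions. Stable control on medication is acceptable". No drug type is named or excluded. The Exclusion Criteria remove significant cardiovascular disease but mention no medicine.

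The mSIM program part of section 3 covers intensity: "The target heart rate zone will be determined by the Karvonen formula". As printed, that formula takes maximum heart rate as 220 minus age, subtracts resting rate to get the reserve, and prescribes 40-60% of it. No other method is offered. The equipment follows the zone: "The resistance level will be pre-set on their bike to meet their aerobic training zone". Participants are taught "the safety reasons for not going above 60%HRR". Staff oversight is by Fitbit, so that "data can be monitored in real-time with the Fitbit data aggregator by research staff".

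Section 4, Medical Record Collection, gathers at screening/baseline "medication types, dosage, and frequencies as well as other existing medical conditions and their treatment". The use it gives for the record concerns participants with outlying data, where "their medical record will be reviewed to identify explanatory factors". Under Baseline in Data Collection and Assessments, an mSIM participant may have to "see a cardiologist for medical management as part of their standard of care if additional ischemic or hypertensive risk factors are uncovered".

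**The concern.** The 60% ceiling protects a participant only if the reserve it is a percentage of is about right. A medicine that limits heart rate can bring true maximum below 220 minus age. The formula then overstates the reserve, and a heart rate labelled 60% is a higher share of what that person actually has.

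Three features of the plan make this matter. Training is at home and unsupervised, so the numeric target carries much of the intensity control; no exercise test or perceived-exertion check is described. Bike resistance is set to reach the same zone. And Fitbit review compares the recorded rate with that zone, so an affected participant who follows instructions appears compliant.

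What is at stake is participant safety: exercise above the moderate level for which the physician gave clearance.

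**Working it through.** The protocol gives no worked heart-rate example, so there is no stated figure to reproduce.

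**Inputs from the protocol.** Maximum M = 220 − age; reserve R = M − resting rate; zone = resting rate + 0.4R to resting rate + 0.6R; eligible ages 50 to 80.

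**Assumed inputs.** Resting rate, and D, the amount by which true maximum falls short of M. The documents give neither.

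**Formulas.** True reserve is R − D. As shares of true reserve, the zone's bottom, midpoint and top are 0.4R/(R − D), 0.5R/(R − D) and 0.6R/(R − D). With D = 0 they return 40, 50 and 60%. The top exceeds 60% exactly when D > 0. The prescribed top lies 0.6D bpm above the rate that is truly 60%, whatever the resting rate.

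**Age 70, resting rate 60.** M = 150, R = 90, zone 96 to 114 bpm.

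| Assumed shortfall | D (bpm) | True reserve | Bottom | Midpoint | Top | Excess at top (0.6D) |
|---|---|---|---|---|---|---|
| 5% | 7.5 | 82.5 | 36/82.5 = 44% | 45/82.5 = 55% | 54/82.5 = 65% | 4.5 bpm |
| 10% | 15 | 75 | 36/75 = 48% | 45/75 = 60% | 54/75 = 72% | 9.0 bpm |
| 15% | 22.5 | 67.5 | 36/67.5 = 53% | 45/67.5 = 67% | 54/67.5 = 80% | 13.5 bpm |
| 20% | 30 | 60 | 36/60 = 60% | 45/60 = 75% | 54/60 = 90% | 18.0 bpm |

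Up to a 10% shortfall the lower half of the zone stays within 60% of true reserve. Only at 20% does the whole zone reach or pass it.

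**Sensitivity to resting rate, age 70.** For the same four shortfalls the top is 65, 71, 77 and 86% at resting rate 50 (R = 100), and 66, 74, 83 and 96% at resting rate 70 (R = 80).

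**Sensitivity to age, resting rate 60.** For D of 10, 20 and 30 bpm the top is 66, 73 and 83% at age 50 (R = 110); 67, 76 and 88% at age 65 (R = 95); and 69, 80 and 96% at age 80 (R = 80).

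**When a rate-limiting medicine does no harm to the zone.** At age 65 and resting rate 60, suppose untreated maximum is 10 bpm above the formula. A medicine that lowers it by 10 bpm leaves D = 0 and the top at 57/95 = 60%. One that lowers it by 20 bpm gives D = 10 and 57/85 = 67%. What counts is where the on-medicine maximum falls relative to 220 minus age.

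**The case against.** The strongest reply is that the plan already places several checks around this. Significant cardiovascular disease is excluded. A physician must clear each participant, and a PARQ+ is completed; neither form is in the documents, so they may already ask about heart-rate-limiting medicines. If an mSIM participant's blood pressure stays too high, the cardiologist must clear the exercise program or the participant is withdrawn. Ramp-up can run to six weeks according to tolerance, and someone who then cannot sustain the zone may be withdrawn. These checks probably reduce how many affected people train and how badly affected they are.

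That stands as mitigation. It does not close the gap, because every check decides whether a person may exercise and none changes the target. The ramp-up criterion asks only whether the formula zone is sustained. In the 20% case above, a participant holding 96 bpm satisfies it while working at 60% of true reserve. Blood pressure checks before sessions are made only if thought necessary, and the weekly calls are for troubleshooting, navigation and homework.

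A second reply is that the top of the zone is its worst point, since the prescription is a range. This is fair, and is why the midpoint is reported too: at shortfalls of 5 and 10% it does not pass 60%.

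A reader might also infer that any heart-rate-limiting medicine pushes the zone over the limit. It does not: on-medicine maximum has to fall below 220 minus age.

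**Conclusion.** The point holds in conditional form. The stated rule can give the wrong target to someone the criteria admit, and the planned monitoring would not show it. For assumed shortfalls of 5 to 20% at age 70 and resting rate 60, the zone top is 65 to 90% of true reserve and the midpoint 55 to 75%. The direction follows from the formula; the sizes rest on assumed shortfalls and resting rates.

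A reader might go further and conclude that some participants will be over-exercised. The documents do not support that. They name no such medicine and give no frequency or size of effect; the number affected may be zero, and no harm from a given excess is shown. Nor does the point count against the ANCOVA comparison in section 6. It is a cheap safety improvement. If the clearance form already covers it, only the protocol wording needs changing.

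**What to change.** 1. Obtain the section 4 medication list at screening, so that it is in hand before randomisation, and add one line to the clearance form asking whether an age-predicted heart rate zone is unsuitable for this person. Flag anyone for whom it is.
2. For those flagged and allocated to mSIM, use a physician-set intensity target in place of 40-60% of reserve: for training, for the pre-set bike resistance, and for the criterion at the end of ramp-up.
3. Ask about medication changes on the existing weekly mSIM calls and after any cardiology management that follows the baseline assessment. Re-check the target if anything has changed.

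The cost is protocol wording, one line on a required form, one question on calls already planned, and occasional clarification with a physician. No visit is added. The training dose in the mSIM arm becomes slightly less uniform. Whether failing the ramp-up criterion should end training only, or participation in the trial, is a separate question and not part of this change.
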